2.1.4.5 Vital signs variables

Vital signs include: heart rate (HR), sitting systolic and diastolic blood pressure, temperature, and respiratory rate (see study flowchart in Appendix E for designated visits). The assessment will be performed after the patient has been seated for at least 5 minutes. Blood pressure and HR will be assessed 3 times with at least 1 minute between each measurement following the 5-minute rest period. The mean of the 3 measurements will be analyzed for each vital sign variable (HR, SBP, and DBP).

2.1.4.6 Physical examination

A complete physical exam will be performed at Visit 1/Screening, Visit 9/Week 26, and Visit 11/Week 52. Results of “Normal”, “Abnormal” or “Not Done” as determined by the Investigator will be reported in the e-CRF by body system.

2.1.4.7 Electrocardiogram variables

12-lead ECG will be performed at Visit 2/Run-in, Visit 9/Week 26, and Visit 11/Week 52. ECG status of “Normal” or “Abnormal” will be reported in the e-CRF as determined by the Investigator.

2.1.4.8 Bone Mineral Density

Bone mineral density of lumbar spine, total hip and femoral neck will be assessed at Visit 3/Week 0 and Visit 11/Week 52.

2.1.5 Pharmacokinetic variables

Pharmacokinetic variables include the concentration of sotagliflozin and sotagliflozin 3-O-glucuronide metabolite in the sotagliflozin group.

2.2 DISPOSITION OF PATIENTS

This section describes patient disposition for both patient study status and the patient analysis populations.

Screened patients are defined as all patients who signed the informed consent.

Randomized patients consist of all patients with a signed informed consent form who have had a treatment kit number allocated and recorded in the IRT database, regardless of whether the treatment kit was used or not.

For patient study status, the total number of patients in each of the following categories will be presented in the clinical study report using a flowchart diagram or summary table:

- Screened patients.
- Run-in patients: patients who had a run-in record in IRT.
- Screen failure patients (including failures during run-in) and reasons for screen failure.
- Nonrandomized but treated patients.
- Randomized patients.
- Randomized but not treated patients.
- Randomized and treated patients.

- Patients who completed the 26-week double-blind core treatment period (see [Section 2.5.4](#)) as scheduled.
- Patients who did not complete the 26-week double-blind core treatment period as scheduled, and the reasons for permanent treatment discontinuation.
- Patients who completed the 52-week entire treatment period as scheduled.
- Patients who did not complete the 52-week entire treatment period as scheduled, and the reasons for permanent treatment discontinuation.
- Patients who have completed the study as scheduled.
- Patients who did not complete the study as per protocol, and the reasons for study discontinuation.
- Patients' end of study status at Week 26 (ongoing, discontinued) and corresponding end of 26-week core treatment status (ongoing, discontinued).
- Patients' end of study status (completed, not completed) and corresponding end of entire treatment status (completed, not completed).
- Status at last study contact.

For screened, run-in, screen failure, and nonrandomized but treated patients, percentages will be calculated using the number of screened patients as the denominator. All other categories of patients will be presented by treatment group and the percentages will be calculated using the number of randomized patients within each treatment group as the denominator. Reasons for treatment discontinuation will be supplied in tables giving numbers and percentages by treatment group. Patients prematurely discontinued from treatment and/or study, along with reasons for discontinuation, will also be listed.

A summary of the distribution of patients by country and center will also be provided (overall number of patients screened, run-in, randomized, and treated, as well as number of patients randomized, discontinued from study treatment, and discontinued from study for each treatment group).

Patients treated but not randomized, randomized but not treated, randomized but not treated as randomized will be identified and described in separate listings. Patients randomized but not treated as randomized will be part of efficacy and safety analyses (see [Section 2.3](#)). Patients randomized but not treated will be included in efficacy analysis. Safety data of patients treated but not randomized will be reported separately.

The randomization strata (HbA1c at Screening [$\leq 8.5\%$, $>8.5\%$], mean SBP at Screening [$<130\text{mmHg}$, $\geq 130\text{mmHg}$, and eGFR at Screening [3A, 3B]) assigned by IRT will be summarized. The percentages will be calculated using the number of randomized patients as the denominator. The discrepancies between the strata assigned by IRT and reported on e-CRF will be listed for all randomized patients.

Kaplan-Meier (KM) plots of the cumulative incidence of double-blind IMP discontinuation due to any reason and due to AEs respectively will be provided for the entire 52-week entire treatment period only (see [Section 2.5.4](#)). A listing of these patients, along with the reason for

discontinuation treatment, study completion status and the reason for discontinuation study, will be provided.

All important deviations including randomization and drug-dispensing irregularities will be summarized in tables giving numbers and percentages of deviations by randomized treatment group.

Additionally, the analysis populations for safety, efficacy, and pharmacokinetics defined in [Section 2.3](#) will be summarized in a table by number of patients in the randomized population.

- Efficacy population: intent-to-treat (ITT) population.
- Safety population.
- Pharmacokinetics population.

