The 26-week core study period is the time from first administration of double-blind IMP to Visit 9/Week 26 (or Day 182 if Visit 9/Week 26 date is missing) or the end of TEAE period for the 26-week double-blind core treatment period (as defined above) whichever is later. This is for defining EOS status at Week 26.

Time to event analysis

For time to event analysis/KM plot, time to event (eg, treatment discontinuation, rescue therapy, hypoglycemia, ESRD, etc) is defined as the number of days from the date of the first administration of double-blind IMP (or the date of randomization if not exposed) to the start date of the first occurrence of the event during the respective analysis period.

Statistical Analysis Plan

Version: Final 3.0

Lexicon Pharmaceuticals Protocol No. EFC14837

Date of Issue: 21 November 2019

Covance Study ID:000000155205

Patients who did not experience any event during the respective analysis period are considered censored observations. The censoring rules are defined below.

Table 5 - Censoring date of time to event for 1st and 2nd step analysis

Time to event	Censoring date at Week 26 (1 st step analysis)	Censoring date at EOT/EOS (2 nd step analysis)
Treatment discontinuation due to any reason	Not applicable	EOT
Treatment discontinuation due to AE	Not applicable	EOT
Time to rescue	min (EOT, Date of W26 visit)	EOT
Time to severe or documented hypoglycemia	See Section 3	Min (EOT+1, EOS)
Time to ESRD	min (EOS, Date of W26/re-allocated W26 eGFR value)	EOS
Time to eGFR decrease	min (EOS, Date of W26/re-allocated W26 eGFR value)	EOS
Time to UACR progression/improvement	min (EOS, Date of W26/re-allocated W26 UACR value)	EOS

Note:

Day 182 will be used if Date of Week 26 visit (or date of W26/re-allocated W26) is not available.

Date of EOS will be used if date of EOT is not available; Last contact date will be used if date of EOS is not available.

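### SAP 2.2 calls the AE-specific discontinuation plot a cumulative incidence, but the planned Kaplan-Meier curve censors other stops and can only equal or exceed it

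*SAP*

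**What the plan says.** SAP 2.2 (Disposition of patients) plans "Kaplan-Meier (KM) plots of the cumulative incidence of double-blind IMP discontinuation due to any reason and due to AEs respectively"; these "will be provided for the entire 52-week entire treatment period only". It refers to SAP 2.5.4 for the definitions.

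SAP 2.5.4 (Time to event analysis) counts days from first dose, or from randomization if the patient was never exposed, "to the start date of the first occurrence of the event during the respective analysis period". For everyone else: "Patients who did not experience any event during the respective analysis period are considered censored observations". Table 5 has a row for "Treatment discontinuation due to AE". Its censoring date is EOT at the second-step analysis, and the first-step column is marked as not applicable. The table note falls back to EOS, then to last contact, if the EOT date is missing.

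The same SAP 2.2 reports disposition by treatment group, where "the percentages will be calculated using the number of randomized patients within each treatment group as the denominator". It adds: "Reasons for treatment discontinuation will be supplied in tables giving numbers and percentages by treatment group".

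Neither document mentions a competing-risk estimator.

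**The concern.** Permanent discontinuation can happen only once. Protocol 10.3.3 lists reasons that need not be AEs, such as the patient's own request or a request from the Sponsor. A patient who leaves IMP for one of these reasons cannot later leave it because of an AE. Censoring that patient at EOT treats the AE stop as still to come, and passes the patient's weight to those still on IMP.

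One minus Kaplan-Meier then estimates the risk of an AE stop in a hypothetical setting where nobody stops for another reason, assuming the two kinds of stop are independent. That is not the cumulative incidence named in SAP 2.2.

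At stake is a safety-related figure. AEs leading to discontinuation are a listed safety endpoint (Protocol 9.2), and readers will compare the curves between arms. The Week 52 value may also differ from the disposition table in the same report, with nothing in the SAP to explain the gap.

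**Working it through.** The documents state no discontinuation rate, so there is no planned figure to reproduce. All rates below are assumptions. The arm size of 260 is from SAP 1.1.

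**Direction.** At each event time let d be the number of AE stops and Y the number still on IMP.
- The Aalen-Johansen estimate rises by S_all × d/Y, where S_all is the proportion that has not stopped for any reason just before that time.
- One minus Kaplan-Meier rises by S_AE × d/Y, where S_AE is the Kaplan-Meier survivor function with other stops censored.
- S_AE is never below S_all, and is above it once any other stop has occurred. One minus Kaplan-Meier is therefore at or above the cumulative incidence, with equality only if no non-AE stop precedes an AE stop.

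**Link to the disposition table.** If nobody is censored before the end of the period except by stopping, S_all = Y/n. Each Aalen-Johansen step is then d/n, and the Week 52 value is the number of AE stops divided by n. That is the disposition percentage when n is the number randomized.

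**Size under constant hazards.** Let a and o be the assumed 52-week proportions stopping for AEs and for other reasons.
- Total cumulative hazard: H = -ln(1 - a - o).
- Kaplan-Meier as planned: 1 - exp(-H × a/(a + o)).
- Example, a = 5% and o = 20%: H = -ln(0.75) = 0.2877; 0.2877 × 0.2 = 0.0575; 1 - exp(-0.0575) = 5.59%, against a true 5.00%.

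| AE stops | Other 5% | Other 10% | Other 20% | Other 30% |
|---|---|---|---|---|
| 5% | 5.13% | 5.27% | 5.59% | 5.97% |
| 10% | 10.27% | 10.56% | 11.21% | 11.99% |

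The relative overstatement is about 3%, 5.5%, 12% and 19-20% across the columns. In absolute terms it runs from 0.13 to 1.99 points.

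**Dependence on timing.** Take 13 AE stops and 52 other stops among 260 patients. If all AE stops come first, Kaplan-Meier gives 13/260 = 5.0%, with no bias. If all other stops come first, it gives 13/(260 - 52) = 13/208 = 6.25%.

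**Simulation check.** I simulated 500 arms of 260 for each of three rate pairs. One minus Kaplan-Meier was never below Aalen-Johansen in the 1,500 arms, and Aalen-Johansen equalled the crude proportion to rounding error. Mean Kaplan-Meier against mean crude proportion:
- 5% AE, 10% other: 5.31% against 5.04%
- 5% AE, 20% other: 5.64% against 5.04%
- 10% AE, 20% other: 11.16% against 9.96%

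**Between-arm difference**, same formula, sotagliflozin minus placebo:

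| Placebo AE/other | Sotagliflozin AE/other | True difference | KM difference | Error (points) |
|---|---|---|---|---|
| 4%/20% | 6%/10% | 2.00 | 6.33 - 4.47 = 1.86 | -0.14 |
| 5%/25% | 8%/15% | 3.00 | 8.69 - 5.77 = 2.92 | -0.08 |
| 3%/15% | 8%/12% | 5.00 | 8.54 - 3.25 = 5.29 | +0.29 |
| 2%/20% | 10%/15% | 8.00 | 10.87 - 2.23 = 8.64 | +0.64 |

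Two arms with the same 5% AE stops but 10% and 20% other stops would show 5.27% and 5.59%, a gap of 0.32 points where the true difference is zero.

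**The case against.** The best defence is that little depends on this plot. It is a disposition figure outside the testing hierarchy of SAP 2.4.4.4, and SAP 2.4.5 keeps the safety analyses essentially descriptive. The crude percentages by reason, a patient listing with reasons and the any-reason curve are all planned, so a reader can recover the true proportion. The SAP states its estimator and censoring rule openly, and a cause-specific Kaplan-Meier curve is a legitimate descriptive quantity if labelled as such. With 260 per arm, one patient is 1/260 = 0.38 points. In the first between-arm scenario the standard error is √(0.04 × 0.96/260 + 0.06 × 0.94/260), about 1.9 points, against an error of 0.14. All of this stands, and it limits the importance of the point. It does not make the curve the quantity that SAP 2.2 names.

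Two stronger readings are tempting, and the documents support neither.
- A reader might infer that more non-AE stopping on placebo would understate the sotagliflozin excess. The inflation also depends on the AE-stop rate. Placebo has more non-AE stops in all four between-arm scenarios, yet the difference is understated in two and overstated in two. No rates are given that would settle the direction.
- A reader might infer that the fix would also bring the curve into line with the TEAE tables. Those use the safety population (SAP 2.4.5.2) by treatment actually received (SAP 2.3.2), whereas disposition uses randomized patients. The two tables can differ from each other whichever estimator is used.

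**Conclusion.** The point holds as a minor one. The estimator does not match the quantity named: the AE-specific curve is never too low, and is too high whenever a non-AE stop precedes an AE stop. It therefore need not match the disposition percentage of randomized patients at Week 52. With 5-10% AE stops, 5-30% other stops and constant hazards, all assumed, the overstatement is about 3-20% of each arm's value, or 0.1-2.0 points. It can be zero if AE stops come first. The between-arm difference can be distorted in either direction, usually by a few tenths of a point. The mechanism follows from the text; the sizes rest on the assumed rates. The any-reason curve is unaffected because every stop counts as an event, and no formal test is touched.

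**What to change.** In SAP 2.2 and Table 5, state that the cumulative incidence of IMP discontinuation due to AE is estimated by the Aalen-Johansen method, with discontinuation for any other reason (including death not counted as an AE stop) as a competing event. Keep Kaplan-Meier for discontinuation due to any reason. If all randomized patients are included and nobody is censored early, the Week 52 value then equals the disposition percentage.

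The minimum alternative is to keep the curve but relabel it as a cause-specific Kaplan-Meier estimate with other stops censored. That corrects the name but leaves the gap from the disposition table.

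The cost is SAP wording and one option in the plotting code. No test, alpha allocation, sample size or patient procedure changes, and Table 5 foresees no first-step version of this plot that would need to be redone.

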2.2.1 Randomization and drug dispensing irregularities

Randomization and drug-dispensing irregularities occur whenever:

1. A randomization is not in accordance with the protocol-defined randomization method, such as a) an ineligible patient is randomized, b) a patient is randomized based on an incorrect stratum, c) a patient is randomized twice, or d) in a dynamic randomization scheme the treatment assignment is, in fact, not random, due to a computer program error.
OR
2. A patient is dispensed an IMP kit not allocated by the protocol-defined randomization, such as a) a patient at any time in the study is dispensed a different treatment kit than as randomized (which may or may not contain the correct-as-randomized IMP), or b) a nonrandomized patient is treated with IMP reserved for randomized patients.

Randomization and drug-dispensing irregularities will be monitored throughout the study and reviewed on an ongoing basis.

All randomization and drug-dispensing irregularities will be documented in the clinical study report. If the number of irregularities is large enough to make a tabular summary useful, the irregularities will be categorized and summarized among randomized patients (number and percentages). Nonrandomized, treated patients will be described separately. Listings with additional, relevant details will be provided in an appendix.

Randomization and drug-dispensing irregularities to be prospectively identified include but are not limited to:

Randomization and drug allocation irregularities

Kit dispensation without IRT transaction

Erroneous kit dispensation

Kit not available

Randomization by error

Patient randomized twice

Stratification error

Patient switched to another site

2.3 ANALYSIS POPULATIONS

Patients treated without being randomized will not be considered randomized and will not be included in any efficacy population.

The randomized population includes any patient who has been allocated to a randomized treatment regardless of whether the treatment kit was used.

For any patient randomized more than once, only the data associated with the first randomization will be used in any analysis population. The safety experience associated with any later randomization will be assessed separately.

The safety experience of patients treated and not randomized will be reported separately, and these patients will not be in the safety population.

2.3.1 Efficacy population

Efficacy analyses will be based on the treatment group allocated by the IRT according to the randomization schedule at randomization visit (as randomized), irrespective of the treatment actually received.

2.3.1.1 Intent-to-treat population

Efficacy analyses will be based on the ITT population, defined as all randomized patients, irrespective of compliance with the study protocol and procedures. Patients will be analyzed for efficacy according to the treatment group to which they are randomized.

2.3.2 Safety population

Safety analyses will be based on the safety population.

The safety population is defined as:

- Randomized patients who receive at least 1 dose of double-blind IMP (regardless of the amount of treatment administered), analyzed according to the treatment actually received.

In addition:

- Nonrandomized but treated patients will not be part of the safety population; however, their safety data will be presented separately.
- Randomized patients for whom it is unclear whether they took the IMP will be included in the safety population as randomized.
- When a patient is exposed to both sotagliflozin and placebo, the patient will be analyzed in the appropriate sotagliflozin group (depending on the treatment kit taken [400 mg or 200 mg]).
- When a patient is exposed to both sotagliflozin 400 mg (treatment kits) and 200 mg (treatment kits), the patient will be analyzed in the sotagliflozin 200 mg group.
- Randomized patients will be excluded from the safety population only if there is documented evidence (ie, all study dates recorded as no medication taken) that patients have not taken the study treatment. If a patient is dispensed double-blind IMP and then lost to follow-up without any documented evidence, the patient will be considered exposed.

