#### 8.1.1 Dose reduction

The dose maintenance will be handled according to the renal function assessed by the creatinine measurement throughout the study. If at any visit after Randomization there is a rise in creatinine level (see details in Section 10.6.2), the Investigator should ensure that no reasonable explanation exists for creatinine increase. Sites will be notified by central laboratory alert if a patient has a >50% increase from Baseline level or >50% above the mean of creatinine values from the last

2 visits, where Baseline level is defined as the mean of creatinine values obtained at Screening and Randomization. The IMP should be stopped for 2 weeks. If at creatinine recheck the patient has returned to the below threshold then IMP will be restarted at a reduced dose (ie, dose reduced via IRT to 200 mg for patients randomized to 400 mg, maintained to 200 mg for patients randomized to 200 mg, and to placebo for patients randomized to placebo). Since IMP received is blinded, patients must return to the site and IRT will be contacted for this IMP re-initiation. Dose reduction can only be obtained at on-site visit by IRT. If the creatinine does not return to below the threshold, the IMP will be permanently discontinued but the patient will be asked to continue attending all study visits.

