#### **10.3.1 Temporary treatment discontinuation with investigational medicinal product**

Temporary treatment discontinuation may be considered by the Investigator because of suspected AEs.

Lower extremity complications (such as skin ulcers, infection, osteomyelitis, and gangrene) requiring treatment should lead to temporary discontinuation of IMP.

If at any visit after Randomization up to Week 8 there is a rise in creatinine level (ie, >50% increase from Baseline level, where Baseline level is defined as the mean of creatinine values obtained at Screening and Randomization) or if at any visit after Week 8 there is a rise of >50% above the mean of creatinine values from last 2 visits, the Investigator should ensure that no reasonable explanation exists for creatinine increase.

The IMP should be stopped for 2 weeks.

Reinitiating of treatment with the IMP will be done under close and appropriate clinical/and or laboratory monitoring once the Investigator has considered according to his/her best medical judgment in the occurrence of the concerned event was unlikely to be related to the IMP and if that the selection criteria for the study are still met (refer to [Section 7.1](#) and [Section 7.2](#)).

If at creatinine recheck the patient has returned to the below threshold then IMP will be restarted at a reduced dose (ie, dose reduced via IRT to 200 mg for those randomized to 400 mg; maintained at 200 mg for those randomized to 200 mg). Since the IMP received is blinded, patients must return to the site and IRT will be contacted for IMP re-initiation.

It is in the interest of the patient to monitor their blood glucose during the temporary discontinuation period, therefore regular determination of SMBG is to be performed and documented (see [Section 9.2.1.8](#)).

For all temporary treatment discontinuations, duration should be recorded by the Investigator in the appropriate pages of the e-CRF when considered as confirmed.

Temporary treatment discontinuation decided by the Investigator corresponds to more than 1 dose not administered to the patient.

Use of any other anti-hyperglycemic medication during the time of temporary treatment discontinuation (ie, insulin during a hospitalization) is to be recorded as concomitant medication with the name and dose recorded in the e-CRF.

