## **10.6.2 Deterioration of renal function**

Patients will be monitored throughout the double-blind Treatment Period and Extension Period for signs of deterioration in renal function (eg, decrease in eGFR or increase in creatinine as defined below) as well as other routine clinical and laboratory findings (see Study Flowchart, [Section 1.2](#)). If at any visit after Randomization up to Week 8 there is a rise in creatinine level (ie,  $> 50\%$  increase from Baseline level, where Baseline level is defined as the mean of creatinine values obtained at Screening and Randomization) or if at any visit after Week 8 there is a rise of  $> 50\%$  above the mean of creatinine values from last 2 visits, the Investigator should ensure that no reasonable explanation exists for creatinine increase and in particular the following causes:

- Medications that increase creatinine
- Decrease in cardiac output
- Obstructive uropathy
- Urinary tract infection
- Volume depletion.

If addressing these causes does not reduce the creatinine level below the above stated threshold, the IMP will be stopped for 2 weeks. The dose will be handled according to the renal function assessed by the creatinine measurement throughout the study and as detailed in [Section 10.3.1](#).

If the creatinine dose not return to below the threshold, then the IMP will be permanently discontinued but the patient will be asked to continue attending all study visits

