2.4.3 Extent of investigational medicinal product exposure and compliance

The extent of IMP exposure and compliance will be assessed and summarized by actual treatment within the safety population ([Section 2.3.2](#)).

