2.4.3.1 Extent of investigational medicinal product exposure

The extent of IMP exposure will be assessed by the duration of IMP exposure.

Duration of IMP exposure is defined in days as last dose date of double-blind IMP - first dose date of double-blind IMP +1, regardless of unplanned intermittent discontinuations (see [Section 2.5.3](#) for calculation in case of missing or incomplete data).

Duration of IMP exposure will be summarized descriptively as a quantitative variable (number of patients exposed, mean, SD, median, minimum, and maximum) during the 26-week core treatment period and 52-week entire treatment period, respectively. In addition, duration of treatment exposure will also be summarized categorically by numbers and percentages for each of the following categories and cumulatively according to these categories:

- 1 to 28 days.
- 29 to 56 days.
- 57 to 84 days.
- 85 to 126 days.
- 127 to 182 days.
- 183 to 364 days.
- and >364 days.

Additionally, the cumulative duration of treatment exposure will be provided, defined as the sum of the duration of treatment exposure for all patients, and will be expressed in patient years.

Number and percentages of patients with dose interruption/reduction due to creatinine increase (identified as those who answered Yes to the question “If Actual Total Daily Dose is 0, was the dose interruption due to creatinine increase per protocol?” in eCRF “Exposure” page) will be summarized.

Number and percentage of patients by final dose at the end of the treatment will also be presented by each treatment group.

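### Read literally, the safety-set rule moves every planned 400 to 200 mg step-down into the 200 mg group, including exposure and events that arose on 400 mg

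*SAP*

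**What the plan says.** SAP 2.3.2 analyses the safety population by treatment actually received and then adds rules for special cases. For a patient exposed to both 400 mg and 200 mg kits, "the patient will be analyzed in the sotagliflozin 200 mg group". Protocol 11.3.2 has the same rule. Neither gives an exception, a time limit or a split by dose.

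The protocol plans this exposure. After a creatinine-triggered stop of 2 weeks, a patient whose value falls back below the threshold restarts, with the "dose reduced via IRT to 200 mg for patients randomized to 400 mg" (Protocol 8.1.1; repeated in 10.3.1). Protocol 10.3.1 adds conditions for restarting: that "the concerned event was unlikely to be related to the IMP and if that the selection criteria for the study are still met".

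Up to Week 8 the trigger is a rise of more than 50% from Baseline. After Week 8 it is a rise of more than 50% "above the mean of creatinine values from last 2 visits" (Protocol 10.6.2).

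On exposure, SAP 2.4.3 states: "The extent of IMP exposure and compliance will be assessed and summarized by actual treatment within the safety population". Within it, SAP 2.4.3.1 plans a count of creatinine-related interruption or reduction, and a final-dose table: "Number and percentage of patients by final dose at the end of the treatment will also be presented by each treatment group".

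**The concern.** A rule that suits a dispensing mistake is worded so that it also covers a planned dose change. The patients moved are not a random sample of the 400 mg arm. They are patients whose creatinine rose on 400 mg far enough to stop treatment, and who then restarted.

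The safety objective (Protocol 5.2) compares each dose with placebo. For events that arose on 400 mg, the rule makes the 400 mg versus placebo difference smaller and the 200 mg versus placebo difference larger. In a trial of CKD stage 3 patients, creatinine is where this matters most.

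**Working it through.** The plan gives no figure for this point, so the check traces the rule through the tables and then computes the shift per patient.

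**1. What moves.**
- All safety analyses use the SAP 2.3.2 population (SAP 2.4.5). AE percentages are taken within its groups (SAP 2.4.5.2).
- Exposure and denominators therefore move for every stepped-down patient, with or without an event. Events and creatinine rows move when present.
- The rule has no period limit. A step-down after Week 26 also moves the patient's 26-week core data, all of it on 400 mg.
- PK samples drawn on 400 mg are summarised under 200 mg, because SAP 2.3.3 refers back to 2.3.2.

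**2. Link to the creatinine rows (SAP 2.4.5.4: at least 30%, 50% and 100% change from baseline).**
- Up to Week 8, the trigger exceeds 1.5 × Baseline and is recorded on 400 mg. It therefore meets the 30% and 50% rows. This holds if the SAP baseline (average of all pre-dose values) equals the trigger Baseline (mean of Screening and Randomization), as it does unless extra pre-dose values exist.
- After Week 8, let r be the mean of the previous two visits divided by Baseline. The trigger is then more than 1.5r × Baseline. It is certain to meet the 50% row only if r ≥ 1, and the 30% row only if r ≥ 1.3/1.5 = 0.867.

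**3. Final-dose table.** Under SAP 2.4.3 with 2.3.2, the 400 mg column holds only patients who never took a 200 mg kit. The cell for 400 mg group with final dose 200 mg is zero by construction. A stepped-down patient appears in the same cell as one kept on 200 mg throughout.

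**4. Shift per moved patient.** Inputs: N = 260 per arm (SAP 1.1); a and b are the patients in the row in the 400 and 200 mg arms; m patients are moved, all in the row.
- Change in 400 mg = (a − m)/(N − m) − a/N
- Change in 200 mg = (b + m)/(N + m) − b/N

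| Row rate (assumed) | m = 1: 400 / 200 mg, points | m = 3: 400 / 200 mg, points |
|---|---|---|
| 2% | −0.378 / +0.375 | −1.14 / +1.12 |
| 10% | −0.347 / +0.345 | −1.05 / +1.03 |

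Example only: 10 versus 5 patients is 3.8% versus 1.9%. With one moved it is 9/259 = 3.5% versus 6/261 = 2.3%. With two moved it is 8/258 = 3.1% versus 7/262 = 2.7%.

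**5. Denominators and exposure.** If an assumed 1%, 2%, 5% or 10% of the 400 mg arm steps down, the 400/200 mg denominators become 257/263, 255/265, 247/273 or 234/286. At 5% (13 patients) with step-down at Week 4, 12 or 26, the 400 mg time counted under 200 mg is 13 × weeks × 7/365.25 = 1.0, 3.0 or 6.5 patient-years.

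**6. Sustained renal events.** Under the SAP 2.5.1 MDRD formula, a 50% creatinine rise gives 1.5^−1.154 = 0.626, a 37% fall in eGFR. A 50% fall in eGFR needs 2^(1/1.154) = 1.823, an 82% rise. SAP Table 3 also asks for a decrease confirmed for at least 30 days without a reversible cause, or positive adjudication. The trigger alone does not meet this, and the moved patients have recovered.

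**The case against.** The strongest reply is that the rule was meant for errors only. It sits among rules for anomalies, such as treated but not randomized. SAP 2.2.1 lists as an irregularity that "a patient at any time in the study is dispensed a different treatment kit than as randomized", as an instance of a kit not allocated by the protocol-defined randomization, and a step-down issued by the IRT need not be one. The planned final-dose table also suggests that the authors expected to see step-downs in the 400 mg group. This is plausible as intent, but no sentence in either document says it, and a programmer following the text would move these patients. If the final-dose table were built by randomized dose it would work, but SAP 2.4.3 says otherwise.

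The second reply is that the route is narrow, and this stands. Under Protocol 10.6.2 the rise must persist after other causes are addressed; the patient must then stop, recover and meet the 10.3.1 conditions. Read literally, those include the entry eGFR of at least 30. By MDRD, a patient at eGFR 40 fails once creatinine is (40/30)^(1/1.154) = 1.28 times baseline, and at eGFR 35 once it is 1.14 times. Protocol 8.1.1 states the restart without these conditions, and the two sections should be reconciled.

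Third, renal summaries on the ITT population (eGFR, decline of more than 50%, ESRD, UACR) are as randomized, and listings show onset date and action taken (SAP 2.4.5.2). That is true, but neither corrects the safety tables.

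Finally, any single-column rule misplaces some time, and regrouping after top-line results is itself a post hoc choice. That bears on how the fix is presented.

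**Conclusion.** Wrong as written. The text gives one clear instruction, and followed literally it counts 400 mg exposure, and any events that arose on it, under 200 mg. It also leaves the final-dose table unable to show the step-down unless that table is built by randomized dose.

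The size is unknown, because the documents give no rate of creatinine rise or restart, and it may be only a few patients. The per-patient shift of about 0.34 to 0.38 points rests on 260 per arm and an assumed row rate of 2% to 10%.

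A reader might infer that every large creatinine rise on 400 mg disappears from that column. The documents do not support this: patients who do not recover, or whose rise resolves without stopping treatment, stay under 400 mg, and events after the step-down did arise on 200 mg. Nor do the documents support the inference that sustained renal events of special interest, ITT renal summaries or efficacy are distorted; these are little or not affected. Safety analyses are descriptive, so no error-controlled result is at stake.

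**What to change.** - In SAP 2.3.2 and Protocol 11.3.2, limit the mixed 400/200 mg kit rule to dispensing errors. Keep patients randomized to and started on 400 mg, whose dose is reduced per protocol, in the 400 mg group, and flag events after the step-down.
- Present the final-dose and creatinine interruption/reduction tables by randomized (starting) dose.
- Summarise PK by the dose taken at each sample.
- SAP 1.6 says top-line results have been reported. Log the change there with date and reason, and show the creatinine PCSA rows, the AE overview and exposure under both the current and the revised grouping.

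The cost is one sentence in each document, a change to the actual-treatment derivation, and a re-run of the safety tables. The downside is that some 200 mg time and events then count under 400 mg, hence the flag. Restart dose and date must come from the IRT kit and exposure records; the e-CRF interruption question in SAP 2.4.3.1 does not give them. No change to the clinical dose-reduction rule is implied.
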